1.3 Schedule of activities

The SoAs provide an overview of the trial visits and procedures. The investigator may conduct unplanned visits in addition to those listed in the SoAs, in order to conduct evaluations or assessments required to protect the wellbeing of the trial subjects.

If, for any reason, subjects are permanently discontinued from the trial before completing all scheduled visits, if possible trial subjects should complete all assessments planned for the Early Termination Visit.

For the SoA for Cohort 5, see Section 13.5.

For Cohorts 1 to 4, Visit 0 to Visit 6 apply for all subjects, Visit 7 to Visit 11 only apply for subjects who consent to a second dose of IMP after issue of protocol version 5.0.

Table 3: Schedule of activities – Cohorts 1 to 4

Activity	Visit 0 (V0)	V1	V1	V2 °	V3	V4	V5	V6 P	V7 P	V8	V9	V10	V11	Early term. Visit	Unscheduled ¹ Potential COVID-19 Illness Visit
Visit description	Screening at ≤28 d pre-V1	Pre-dose	Dose 1 (D1)	3 d post-D1	7 d post-D1	28 d post-D1	3 m FU post-D1	6 m FU post-D1	Dose 2 (6 to 7 m post-D1)	7 d post-D2	28 d post-D2	3 m FU post-D2	6 m FU post-D2		
Days relative to Dose 1	N/A	1	1	3	8	29	90	180						N/A	N/A
Permitted visit window				+2 d	+2 d	±3 d	±7 d	-10 d to +30 d	+30 d post-V6	+2 d from 7 d post-D2	±3 d from 28 d post-D2	±7 d from 3 m post-D2	±10 d from 6 m post-D2		
Maximum total blood volume (mL) drawn per visit	25	175	0	15	170	155	155	155		170	155	155	155	155	65

- a. Brief (symptom-directed) physical examination as indicated.
- b. At 1 h (±15 minutes) before and after dosing.
- c. Vital signs: systolic/diastolic blood pressure, pulse rate, respiratory rate, and oral body temperature.
- d. Dipstick urine analysis: For details of all assessed urine clinical laboratory parameters, see Section 10.3.
- e. Viral screen: screen for human immunodeficiency virus (HIV)-1 and HIV-2, Hepatitis B, and Hepatitis C.
- f. Clinical laboratory tests: Chemistry and hematology. Only in women who are not VOCBP (to confirm postmenopausal status): follicle stimulating hormone at Visit 0. Only for VOCBP: serum β-HCG at Visit 0. For details of all assessed blood clinical laboratory parameters, see Section 10.3.

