- g. In VOCBP: The serum β-HCG pregnancy test at Visit 0 will be performed using the sample collected for clinical laboratory tests. Before each dosing, urine pregnancy tests will be performed using a commercial kit at the site and the trial subjects will be counseled about the need for consistent and correct use of a highly effective method of contraception.
- h. Leftover blood after completion of the assessments may be used for additional biomarker analyses and/or development of analytical methods.
- i. Trial site personnel will remind the subjects to record the oral body temperature and the worst grade for each symptom in the e-diary at approximately the same time every evening on the day of IMP administration and then every day in the evening for a total of seven consecutive days. Ask/remind the subject to contact the site if they experience any severe or potentially life-threatening reactogenicity events. Trial site personnel will remind the subjects to record the use of antipyretic/analgesic medication to treat symptoms associated with IMP administration for 7 d after each IMP dose using the e-diary.
- j. Only SAEs, adverse event(s) of special interest, AEs that lead to discontinuation or withdrawal, and AEs linked to confirmed COVID-19 cases will be recorded. SAEs must be recorded upon awareness.
- k. For FU visits, only any prohibited medication (including SARS-CoV-2 non-trial vaccinations) will be recorded.
- l. Optimally within 3 d after potential COVID-19 illness onset. All known NAAT-based SARS-CoV-2 positive subjects, from randomization until end of trial, will be asked for an additional unscheduled visit to define the COVID-19 illness as per Section 8.2.8. The COVID-19 illness visit will define the illness as either confirmed COVID-19, unconfirmed COVID-19, or confirmed severe COVID-19.
- m. The results must be available prior to administration of trial treatment at Visit 1.
- n. Blood samples for CCI assessment at "Potential COVID-19 Illness Visit" should only be collected if the visit occurs more than 2 months after the last IMP dose.
- o. This visit will apply to sentinel subjects only.
- p. Visit 6 and Visit 7 can (should ideally) occur on the same day.

- q. Informed consent can be obtained for Dose 2 at either Visit 5, 6 or Visit 7.
- r. Only for subjects that received BNT162b2 Bivalent + BNT162b4 for Dose 1 and who consented to a second (Dose 2).
- s. To be completed before administration of Dose 2.

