3 OBJECTIVES AND ENDPOINTS

Objectives, estimands and endpoints – Cohorts 1 to 4

OBJECTIVES	ESTIMAND *	ENDPOINTS
Primary objectives		
To describe the safety and tolerability of one and two doses of BNT162b4 + BNT162b2 Bivalent, one dose of BNT162b4 + BNT162b2 Monovalent (OMI XBB.1.5) as a booster, or one dose of BNT162b2 Bivalent alone at each applicable DL in healthy adults aged 18 years and older, with and without evidence of prior SARS-CoV-2 infection who previously received at least three prior doses of an authorized RNA-based COVID-19 vaccine.	For each DL cohort, the frequency of dosed subjects with: 
Solicited local reactions at the injection site recorded up to 7 d after every IMP dose.Solicited systemic events recorded up to 7 d after every IMP dose.Subjects with at least one AE occurring up to 28 d after every IMP dose.Subjects with at least one SAE occurring up to 6 months after every IMP dose.	
Solicited local reactions (pain, erythema / redness, induration / swelling)Solicited systemic events (vomiting, diarrhea, headache, fatigue, myalgia, arthralgia, chills and fever)AEsSAEs
	For each DL cohort, the percentage of dosed subjects with: 
Abnormal hematology or chemistry laboratory values 3 d (Dose 1 sentinel group only) and 7 d after every dose.Grading shifts in hematology or chemistry laboratory assessments between baseline and 3 d (Dose 1 sentinel group only) and 7 d after every IMP dose.	
Hematology and chemistry laboratory parameters (see Section 10.3)
	For each DL cohort, the percentage of dosed subjects with: 
New ECG abnormalities 3 d (Dose 1 sentinel group only) and 7 d after every IMP dose.	
ECG abnormalities consistent with probable or possible myocarditis or pericarditis as defined in the protocol
Secondary objectives		

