8.3.1 Time period and frequency for collecting AE and SAE information

All AE related information will be collected at the timepoints specified in the SoAs (Section [1.3](#) and Section [13.5](#)).

Non-serious AEs will only be collected as of first IMP dose administered while SAEs need to be recorded upon awareness starting once informed consent is given.

For Cohorts 1 to 4, AE collection will start from Visit 0 and continue until Visit 4 (i.e., until 1 month follow-up post-Dose 1), and (for subjects who consent to a second dose of IMP after issue of protocol version 5.0) restart from Visit 7 and continue until Visit 9 (i.e., until 1 month follow-up post-Dose 2).

For Cohort 5, AE collection will start from Visit 0 and continue until Visit 9 (1 month post-Dose 2).

AESIs, SAEs, AEs that lead to trial subject discontinuation or withdrawal, and all AEs linked to confirmed COVID-19 cases will be recorded up to the last planned visit for subjects who consent to a second dose of IMP. For subjects in Cohorts 1 to 4 completing Dose 1 only, recording will continue until Visit 6 (6 months post-Dose 1). For subjects in Cohort 5 completing Dose 1 only, recording will continue until the last scheduled visit (5 months post-Dose 1).

Medical occurrences that begin after obtaining informed consent but before the start of trial treatment administration must be recorded on the respective Medical History/Current Medical Conditions section of the CRF and not in the AE section unless they qualify as SAEs.

Medical occurrences meeting the criteria for an SAE (see Section [10.4.2](#)) must be reported as SAEs (see Section [8.3.4](#)).

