8.3.2 Detecting and reporting AEs and SAEs

The investigator and any qualified designees are responsible for detecting, documenting, and reporting events that meet the definition of AEs or SAEs, and remain responsible for following up all AEs and SAEs. The investigator will record on the CRF all AEs and SAEs observed directly and all AEs and SAEs spontaneously reported by the trial subject.

Open-ended and non-leading verbal questioning of the trial subject is the preferred method to inquire about AE occurrences. Care will be taken not to introduce bias when detecting AEs and/or SAEs.

Guidance for the recording, evaluating, and assessing of AEs and SAEs is provided in Section [10.4](#).

For grading the severity of AEs and SAEs, the US FDA “[Toxicity Grading Scale for Healthy Adult and Adolescent Volunteers Enrolled in Preventive Vaccine Clinical Trials](#)” will be used.

Investigators are not obligated to actively seek AE or SAE after conclusion of the trial participation. However, if the investigator learns of any SAE, including a death, at any time after a trial subject has been discharged from the trial, and he/she considers the event to be related (see Section 10.4) to the trial treatment or trial participation, the investigator must promptly notify the sponsor as described in Section 10.4.4.

The investigator may be requested by the sponsor to obtain specific follow-up information in an expedited fashion.

All SAEs (initial and follow-up reports) will be recorded and reported to the sponsor or designee within 24 h after the site becoming aware of the event, as indicated in Section 10.4.4.

For real time monitoring of events which contribute to pausing rule criteria (see Section 7.1.1), all such events (even if non-serious) need to be reported on the SAE form within 24 h of awareness as described in Section 10.4.4.

AESIs have been defined in this trial. For how to report AESIs, see Section 8.3.8.

8.3.3 *Follow-up of AEs and SAEs*

After the initial AE/SAE report, the investigator is required to proactively follow up with each trial subject at subsequent visits/contacts.

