### 6.5.1.3 Adverse events

Non-serious AEs will only be collected as of first IMP dose administered while SAEs need to be recorded upon awareness starting once informed consent is given. For Cohorts 1 to 4, AE collection will start from Visit 0 and continue until Visit 4 (i.e., until 1 month follow-up post-Dose 1), and (for participants who consent to a second dose of IMP after issue of

protocol version 5.0) restart from Visit 7 and continue until Visit 9 (i.e., until 1 month follow-up post-Dose 2). For Cohort 5, AE collection will start from Visit 0 and continue until Visit 9 (1 month post-Dose 2). AESIs, SAEs, AEs that lead to trial participant discontinuation or withdrawal, and all AEs linked to confirmed COVID-19 cases will be recorded up to the last planned visit for participants who consent to a second dose of IMP. For participants in Cohorts 1 to 4 completing Dose 1 only, recording will continue until Visit 6 (6 months post-Dose 1). For participants in Cohort 5 completing Dose 1 only, recording will continue until the last scheduled visit (5 months post-Dose 1).

Summary tables will include AEs reported from each IMP administration up to 28 days after each IMP administration, SAEs and AESIs occurring from IMP Dose 1 up to 6 months after each IMP administration for participants in Cohorts 1 to 4 and SAEs occurring from IMP Dose 1 up to 3 months after last IMP administration for participants in Cohort 5. AEs leading to IMP discontinuation or trial withdrawal will be listed, and summarized when at least 10 events in all participants have been reported.

AEs/SAEs post-Dose 1 will be summarized by treatment group post-Dose 1 based on the Safety Set. AEs/SAEs post-Dose 2 will be summarized by treatment group post-Dose 2 based on Dose 2 Safety Set.

All AEs will be coded using the most recent version of the MedDRA® coding system and graded for severity using FDA guidance for “[Toxicity Grading Scale for Healthy Adult and Adolescent Volunteers Enrolled in Preventive Vaccine Clinical Trials](#)”. No imputation for missing grades will be performed.

If an AE is reported more than once for the same participant for a SOC / PT the AE will be counted once for this SOC / PT for the specified reporting period.

All AE (from post-dose) summary tables will be sorted alphabetically by SOC and PT within SOC, unless specified otherwise.

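### AE and SAE collection ends at visits that may fall before the 28-day and 6-month (Cohort 5: 3-month) endpoint windows close, with no catch-up, so the primary safety rates can be slightly undercounted

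*Protocol*

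**What the plan says.** Protocol section 3 sets the primary estimands for Cohorts 1 to 4 as "Subjects with at least one AE occurring up to 28 d after every IMP dose" and "Subjects with at least one SAE occurring up to 6 months after every IMP dose". For Cohort 5 (section 13.6) the SAE window is 3 months after the last dose.

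Collection is defined by visit. Protocol 8.3.1 states for Cohorts 1 to 4 that "AE collection will start from Visit 0 and continue until Visit 4 (i.e., until 1 month follow-up post-Dose 1"); it restarts at Visit 7 and ends at Visit 9. In Cohort 5 it runs without a break to Visit 9. SAE recording runs to the last planned visit for those who consent to Dose 2. Otherwise: "For subjects in Cohorts 1 to 4 completing Dose 1 only, recording will continue until Visit 6 (6 months post-Dose 1").

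The schedules of activities allow these visits to be early. Visit 4 is Day 29 ±3 d, and Visit 9 is plus or minus "3 d from 28 d post-D2". Visit 6 is Day 180 with −10 to +30 d, Visit 11 is 6 months after Dose 2 ±10 d, and Cohort 5 Visit 10 is 3 months after Dose 2 ±7 d.

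At Visits 5, 6, 10 and 11 (marked with footnote j in SAP Appendix 4) recording is limited by Protocol Table 3 footnote j: "Only SAEs, adverse event(s) of special interest, AEs that lead to discontinuation or withdrawal, and AEs linked to confirmed COVID-19 cases will be recorded". The Cohort 5 schedule has no ordinary-AE entry at Visit 10. After participation ends, "Investigators are not obligated to actively seek AE or SAE after conclusion of the trial participation" (Protocol 8.3.2).

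SAP 6.5.1.3 tabulates "AEs reported from each IMP administration up to 28 days after each IMP administration". SAP 6.1.1 divides by all participants in the analysis set.

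**The concern.** The endpoint is a fixed number of days after dosing, but the end of collection floats with the visit. When Visit 4 or Visit 9 is held 25 days after the dose, an ordinary AE starting on days 26 to 28 belongs to the endpoint, yet no later visit is asked to record it. A late visit does not make up for this, because the SAP cuts the table at 28 days. The same applies to SAEs that start after an early final SAE visit. The denominator takes no account of days observed, so any error runs towards undercounting.

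These are the primary endpoints of a first-in-human trial, and the only quantitative support for its sample size is the chance of seeing at least one AE (Protocol Table 6).

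**Working it through.** **1. The plan's own figure.** Table 6 uses P(at least one) = 1 − (1 − p)^N. For p = 0.02: 1 − 0.98^90 = 0.838 (stated 0.84) and 1 − 0.98^45 = 0.597 (stated 0.60). All 15 cells reproduce.

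**2. Gaps.** Gap = end of window minus days from dose to visit. Day 29 is 28 d after a Day 1 dose, so Visit 4 falls 25 to 31 d after Dose 1. Visit 6 on Day 170 is 169 d after Dose 1. The mean gap assumes visits spread evenly over the permitted days, which the documents do not state.

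| Last collection visit | Window length | Largest gap | Mean gap |
|---|---|---|---|
| V4 (Cohorts 1–4), V9 (all cohorts) | 28 d | 3 d (10.7%) | (3+2+1)/7 = 0.86 d (3.1%) |
| V6, 6 months = 168 d | 168 d | 0 d | 0 d |
| V6, 6 months = Day 180 | 179 d | 10 d (5.6%) | 55/41 = 1.34 d (0.7%) |
| V6, 6 months = 6 × 30.4375 d | 182.6 d | 13.6 d (7.5%) | 2.43 d (1.3%) |
| V11 | 6 months after Dose 2 | 10 d (about 5.5%) | 55/21 = 2.62 d (1.4%) |
| V10, Cohort 5 | 3 months after Dose 2 | 7 d (about 7.7%) | 28/15 = 1.87 d (about 2%) |

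The three lengths for 6 months come from Protocol 6.5.1 (168 d, for non-trial COVID-19 vaccines), the schedule of activities (Day 180) and the days-to-months conversion in SAP 6.1.2. Visit 4 ends ordinary AE collection only in Cohorts 1 to 4.

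**3. Effect on the AE rate.** Assume a constant hazard and read Table 6's rate as a 28-day rate. With a share f of the window observed, captured rate = 1 − (1 − p)^f. For p = 2%:

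- Every visit at 25 d: f = 25/28, captured 1.79%; detection 0.80 (N=90) and 0.56 (N=45).
- Evenly spread visits: f = 1 − 0.857/28 = 0.969, captured 1.94%; detection 0.83 and 0.59.

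**4. Effect on the SAE rate after Dose 1.** Take the 90 planned controls (6 × 15), who all stop at Visit 6, and p = 2%, so 1.80 expected.

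- Every Visit 6 on Day 170: 1.89% captured against Day 180 (1.70 expected, 0.10 lost), or 1.85% against 182.6 d (1.67 expected, 0.13 lost).
- Evenly spread visits, Day 180: 1.985%.

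**5. Difference by arm after Dose 1.** Ordinary AE collection stops at Visit 4 in both arms. For SAEs, controls and BNT162b4 recipients without Dose 2 both stop at Visit 6. A Dose 2 recipient with an early Visit 6 and a later Visit 7 (allowed up to 30 d after) is asked about the interval at Visit 7. If every control were seen on Day 170 and no BNT162b4 recipient lost a day, the difference at a 2% rate would be 2.00 − 1.89 = 0.11 to 2.00 − 1.85 = 0.15 percentage points. That is a ceiling.

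**The case against.** The footnote to the objectives tables (Protocol 1.1 and 3, SAP 1.1) says the assessments behind the estimands take place within the visit windows, and 8.3.1 labels each stop visit with its nominal period. On that view this is ordinary visit tolerance. The point carries weight: the sponsor accepted some slack. But the footnote governs when assessments are done; it does not alter an endpoint that counts events up to 28 days, and the SAP still cuts late visits at that day.

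Safeguards also narrow the gap. AESIs, AEs leading to discontinuation and COVID-linked AEs continue past Visits 4 and 9, as do SAEs, which are recorded on awareness. Related SAEs stay reportable after the observation period (Protocol 8.3.2 and 10.4.4). What can be lost is other non-serious AEs starting in the last 3 days of a window, and mainly unrelated SAEs at its end.

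A reader might infer three stronger things that the documents do not support:

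- **That the rates are undercounted as a matter of course.** Loss needs an early visit, and the documents do not say how many visits were early.
- **That Visit 6 costs 13.6 days.** That is one of three lengths for 6 months; with 168 d there is no gap.
- **That SAEs after Dose 1 are collected unequally by arm.** SAP 6.5.1.3 closes the post-Dose 1 period at Dose 2, Table 3 footnote p says Visits 6 and 7 should ideally coincide, and BNT162b4 recipients without Dose 2 stop at Visit 6 as controls do. A difference arises mainly when Visit 6 is early and Dose 2 follows later. However, the Safety overview list in the same SAP section takes SAEs through 6 months after each dose. On that reading, SAEs after Dose 2 could still count towards Dose 1. The two statements need reconciling.

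**Conclusion.** The point stands in a limited form. Each visit that ends collection, apart from Visit 6 if 6 months means 168 d, may precede the end of its endpoint window, and no catch-up is specified. Following the plan can lose events from the primary AE and SAE rates but cannot add any. The loss per participant is at most 3 of 28 days for AEs; for SAEs it is 0, 10 or 13.6 days at Visit 6, up to 10 at Visit 11 and up to 7 at Cohort 5 Visit 10. With evenly spread visits it averages about 1 to 3% of a window, and nothing at Visit 6 if 6 months means 168 d. The effect on captured rates and on Table 6 is small even in the worst case, and any difference by arm is smaller still. These sizes rest on a constant hazard and, for the averages, on an even spread of visits; events clustered soon after dosing would make the loss smaller. No hypothesis is tested, so no type I error or power is affected. It merits correction because the endpoints are primary and the remedy is cheap.

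**What to change.** 1. In Protocol 8.3.1 and footnote j, define the AE and SAE windows in days after dose, with one length for 6 months.
2. At Visits 5 and 10 (including Cohort 5 Visit 10), also record any AE not yet recorded whose onset was within 28 d of the preceding dose.
3. When the last SAE visit (Visit 6 without Dose 2, Visit 11, Cohort 5 Visit 10) was held early, add a brief telephone SAE check at the end of the window, applied alike in both arms.
4. In SAP 6.5.1.3, reconcile the post-Dose 1 period that ends at Dose 2 with the SAE table running 6 months from each dose, and report by treatment group how many participants had incomplete windows. For visits already held, this is the part that can still be done.

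Forbidding an early Visit 6 only for participants without Dose 2 is not advisable. Consent to Dose 2 may come as late as Visit 7 (footnote q), and controls would then tend to have a later Visit 6 than Dose 2 recipients, which could itself make follow-up differ by arm.

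The cost is one extra question at an existing visit, with some recall error, a short call for early visits, and one added SAP table.

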8.3.2 Detecting and reporting AEs and SAEs

The investigator and any qualified designees are responsible for detecting, documenting, and reporting events that meet the definition of AEs or SAEs, and remain responsible for following up all AEs and SAEs. The investigator will record on the CRF all AEs and SAEs observed directly and all AEs and SAEs spontaneously reported by the trial subject.

Open-ended and non-leading verbal questioning of the trial subject is the preferred method to inquire about AE occurrences. Care will be taken not to introduce bias when detecting AEs and/or SAEs.

Guidance for the recording, evaluating, and assessing of AEs and SAEs is provided in Section [10.4](#).

For grading the severity of AEs and SAEs, the US FDA “[Toxicity Grading Scale for Healthy Adult and Adolescent Volunteers Enrolled in Preventive Vaccine Clinical Trials](#)” will be used.

Investigators are not obligated to actively seek AE or SAE after conclusion of the trial participation. However, if the investigator learns of any SAE, including a death, at any time after a trial subject has been discharged from the trial, and he/she considers the event to be related (see Section 10.4) to the trial treatment or trial participation, the investigator must promptly notify the sponsor as described in Section 10.4.4.

The investigator may be requested by the sponsor to obtain specific follow-up information in an expedited fashion.

All SAEs (initial and follow-up reports) will be recorded and reported to the sponsor or designee within 24 h after the site becoming aware of the event, as indicated in Section 10.4.4.

For real time monitoring of events which contribute to pausing rule criteria (see Section 7.1.1), all such events (even if non-serious) need to be reported on the SAE form within 24 h of awareness as described in Section 10.4.4.

AESIs have been defined in this trial. For how to report AESIs, see Section 8.3.8.

8.3.3 *Follow-up of AEs and SAEs*

After the initial AE/SAE report, the investigator is required to proactively follow up with each trial subject at subsequent visits/contacts.

All AEs and SAEs will be followed up until resolution, stabilization, the event is otherwise explained, or the trial subject is lost to follow-up, or the trial subject withdraws consent (as defined in Section 7.3). If no final status is reached by the last planned follow-up visit, the investigator must confirm the unavailability of a final status. Further information on follow-up procedures is provided in Section 10.4.2.2.

The investigator is obligated to perform or arrange for the conduct of supplemental measurements and/or evaluations as medically indicated or as requested by the sponsor to elucidate the nature and/or causality of the AE or SAE as fully as possible. This may include additional laboratory tests or investigations, histopathological examinations, or consultation with other health care professionals.

New or updated information will be recorded in the originally completed CRF.

If a trial subject dies during participation in the trial or during a predefined follow-up period (see the SoAs in Section 1.3 and Section 13.5), the investigator will provide the sponsor a copy of any postmortem findings including histopathology.

The investigator will submit initial and follow-up SAE reports to the sponsor or designee within 24 h after the site becoming aware of the event, as indicated in Section 10.4.4.

8.3.4 *Reporting requirements for SAEs including SUSARs*

Prompt notification of an SAE via an EDC system and/or the provided SAE form by the investigator to the sponsor within 24 h of the site's awareness is essential so that the ethical responsibilities to trial subjects, the safety of a trial treatment under clinical investigation, and regulatory reporting obligations can be met.

The sponsor has a legal responsibility to notify both the local regulatory authority and other regulatory agencies involved in the conduct of trials with the same IMP about the safety of a trial treatment under clinical investigation. The sponsor will comply with country-specific regulatory requirements relating to safety reporting to the regulatory authority, Institutional Review Boards (IRBs)/Independent Ethics Committees (IECs), and investigators. The execution of reporting to the different entities may be delegated as detailed in the trial-specific Safety Management Plan.

All serious adverse reactions where the nature, severity or outcome is not consistent with the reference safety information are “unexpected serious adverse reactions”. The expectedness assessment for all related SAEs is based on the reference safety information included in Section 6.1.5 of the [BNT162 IB](#) and the [BNT162b4 IB](#).

All suspected adverse reactions related to an IMP (the tested drugs and comparators) that occur in this trial, and that are both unexpected and serious, qualify as SUSARs. SUSARs are subject to expedited reporting by the sponsor according to applicable regulatory requirements and guidance (i.e., ICH E2A guidance). Information about analysis of similar events will be added to the SUSAR report. IRBs/IECs will receive SUSAR reports as applicable.

8.3.5 *Pregnancy testing and handling of pregnancies*

For VOCBP, pregnancy tests will be performed at the times given in the SoAs (Section [1.3](#) and Section [13.5](#)).

For all trial subjects, pregnancy information will be collected over the time period defined in SoAs (Section [1.3](#) and Section [13.5](#)).

Any female trial subject who becomes pregnant while participating in the trial will need to discontinue the IMP immediately.

Pregnancy information will only be collected after obtaining written informed consent from the pregnant female trial subject (or if a male trial subjects' partner becomes pregnant, written informed consent from the trial subjects' partner).

If a pregnancy is reported, the investigator should inform the sponsor within 24 h of learning of the pregnancy and should follow the procedures outlined in Section [10.5.3](#).

Pregnancy *per se* is not an AE (and hence not an SAE). Abnormal pregnancy outcomes (e.g., spontaneous abortion, fetal death, stillbirth, congenital anomalies, ectopic pregnancy) are considered SAEs.

As described in Section [7.1.2](#), trial subjects who become pregnant will be permanently discontinued from trial treatment and will not have further blood draws, but will otherwise complete all planned assessments, if required including pregnancy follow-up as described in Section [10.5.3](#).

8.3.6 *Death events*

Any death that occurs within the observation period will be reported as an SAE, if not covered by the exemptions to the SAE definition as defined in Sections [8.3.7](#), [10.4.2](#), and [10.4.2.2](#), which do also apply for fatal cases. Date and cause of death will be recorded. If available, a copy of an autopsy report should be submitted upon request.

In case of a fatal event, the event term should not be “death” but the underlying event which led to death (death = outcome). If there is more than one AE in a fatal case, only for the AE leading the outcome “fatal” (death) should be selected. If the cause of death is unknown and cannot be ascertained at the time of reporting, “unexplained death” should be documented as event term.

In addition to reporting as SAE, the death page of the CRF needs to be completed.

8.3.7 *Disease-related events/outcomes not qualifying as AEs or SAEs*

Not applicable.

8.3.8 *Adverse events of special interest (AESIs)*

An AESI, serious or non-serious, is one of scientific and medical concern specific to the sponsor's product or program, for which ongoing monitoring and rapid communication by the investigator to the sponsor are appropriate. Such an event might warrant further investigation in order to characterize and understand it. Depending on the nature of the event, rapid communication by the trial sponsor to other parties (e.g., regulators) might also be warranted.

The following will be reported as AESIs:

- Anaphylaxis
- Thromboembolic events (e.g., deep vein thrombosis, stroke, myocardial infarction)
- Immune thrombocytopenia
- Immune-based neurologic events (e.g., optic neuropathy, Guillain-Barré syndrome)
- Myocarditis (all Levels of Certainty including “Possible cases” (1 to 3) as per Brighton Collaboration Case Definition),
<https://brightoncollaboration.org/myocarditis/>
- Pericarditis (all Levels of Certainty including “Possible cases” (1 to 3) as per Brighton Collaboration Case Definition),
<https://brightoncollaboration.org/myocarditis/>

All symptoms that could represent myocarditis or pericarditis should be reported within 24 h of awareness using the dedicated Myocarditis or Pericarditis AESI Report Form and reporting to the contact details provided in Section 10.4.4. For guidance on the management of symptoms that could represent myocarditis or pericarditis, see Section 12.2.

All other AESIs, excluding myocarditis and pericarditis, (even if non-serious), should be reported within 24 h of awareness as well, using the AESI Report Form and reporting to the contact details provided in Section 10.4.4. However, if such AESI meets the serious criteria, it must be reported on the SAE form within 24 h of awareness as described in Section 10.4.4.

All AESIs will be followed up until resolution, stabilization, the event is otherwise explained, or the trial subject is lost to follow-up (as defined in Section 7.3).

